Report and Manuscript Preparation		---

7. Study Endpoints

The primary endpoints for the pilot trial are intervention **acceptability** and **feasibility**. To assess **intervention acceptability** we will measure patients' satisfaction with the interventions with a revised version of the Client Satisfaction Questionnaire,⁵⁸⁻⁶⁰ where higher satisfaction will indicate greater intervention acceptability, and the System Usability Scale (SUS),⁶¹ where higher scores indicate ease of usability. We will assess questionnaire acceptability using open-ended patient questions. In addition to quantifying **feasibility** using **recruitment and retention rates**, to provide concrete estimates of the expected rates of missing data and participant attrition, we will keep a detailed log of relevant factors that could create barriers to subsequent study completion. We will measure time spent sedentary (sitting/lying), standing, and stepping (and the intensity) during awake hours with the activPAL3 accelerometers, and compare these values between the IMPACT and UC groups. Time required for study participation will be measured using survey completion times as well as intervention session time estimates.

In addition to the primary endpoints noted above, we will assess the feasibility and acceptability of collecting a number of patient outcomes that will be the key target outcomes in a large scale R01. A systematic review of 35 randomized controlled trials of exercise training in solid organ transplant recipients, including 9 kidney, 21 heart, 3 lung, and 2 liver transplant studies, found that there were a total of 62 patient outcome measures, including peak VO₂, SF-36 score, and muscle strength.⁵² Of these, our team determined that the most relevant outcomes to assess in our pilot include: (a) variables that we will gather from participants' medical records (i.e., % weight change, lipid profile, and HbA1c); (b) patient reported outcomes, including the PROMIS Sleep Related Impairment⁶² and Sleep Disturbance⁶³ Measures and PROMIS Global Health⁶⁴; and, (c) occupational functioning, using the occupation subscale of the CHART-SF.⁶⁵ The CHART-SF is the most widely used participation measure in rehabilitation research,⁶⁶ and has been used in various ethnic groups.⁶⁷

8. Research Setting

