Questionnaires: Questionnaires will be delivered via Twistle or REDcap. See Appendix F for Twistle Script listing all comments being used throughout the study that will be delivered according to the relevant questionnaire and the timeline in Fig. 2. Brief surveys will be conducted over the phone.

In-Depth Interviews with Participants. We will conduct interviews with participants in the IMPACT condition, either in-person, over the phone or via HIPAA compliant Zoom, and focus on participants' experience with the intervention and recommendations for improvement (Appendix D). Interviews will be recorded and transcribed for analysis.

Periodic Survey. Periodically, the Project Coordinator will contact clinical, and administrative teams asking to what extent, if any, barriers and/or facilitators to the intervention they have observed or experienced and suggestions for change if indicated. We will ask the transplant team to elicit feedback on the intervention process and provide any feedback to the Project Coordinator. We will elicit impressions of the IMPACT intervention and solicit suggestions regarding optimizing the future large-scale study (Appendix D). The Project Coordinator also will document all observations and experiences in a log (Appendix E), noting the date and source of the observation. We will review the log during research team standing meetings, and identify need for process changes. We will then communicate the problems identified and planned changes to the research, clinical and administrative teams. We will capture this data in REDCap, either over the phone or via direct link, whichever is more convenient for the team member. Interviews conducted over the phone will be recorded and transcribed.

Types of data

In addition to the in-depth interviews and brief/periodic surveys, we will collect data using questionnaires and from medical records. We selected the measures (see Appendix C for all measures) for data collection because they (a) are widely used in organ donation

PROTOCOL TITLE: **Improving Healthcare Outcomes in American Indian and Hispanic Transplant Recipients Using Culturally-Tailored Novel Technology (IMPACT)**

and/or transplantation studies, other medical populations, or both; (b) have known psychometric properties, including (for scaled measures) Cronbach's α 's of $\sim .80\text{-.92}$ (see references cited with each instrument for psychometric data); and/or (c) used in our previous research.

Outcomes

1. Questionnaires

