Clinical team and administrators' surveys will remain anonymous. Informed consent will be obtained from all participating staff before the start of the first survey via consent letter. Data from these surveys will also be kept confidential.

The study team will follow COVID safe practices as outlined in the related attachment.

19. Potential Benefits to Subjects

Benefits include: reducing the likelihood of weight gain, diabetes, and cardiovascular events post-transplant. Participation in the study will address the limitations of previous physical activity and dietary interventions in KT recipients: (1) small sample size, (2) short patient follow-up, and (3) limited population diversity. Finally, participants will benefit from knowing that they will be helping future patients and other transplant centers easily package and disseminate the intervention using Twistle, which gives them a way to tailor the intervention to the needs of their specific patient population and maintain regular interaction and follow-up.

20. Recruitment Methods

Flyers will be placed and brochures in the UNM HSC Transplant Center. In addition, potential participants will be approached shortly before or after undergoing KT, as they are in recovery, at the UNM HSC Transplant Center. All participants will continue to receive care according to national standards whether or not they participate in the study. All participants who are randomized to the IMPACT intervention will have in-depth interviews. All IMPACT intervention study staff, transplant clinic staff and key administrators involved in the transplant process will be recruited for post-intervention surveys at the time of study initiation.

21. Provisions to Protect the Privacy Interests of Subjects

Face-to-face visits will take place at the UNM HSC Transplant Center in private clinic rooms.

22. Economic Burden to Subjects

PROTOCOL TITLE: **Improving Healthcare Outcomes in American Indian and Hispanic Transplant Recipients Using Culturally-Tailored Novel Technology (IMPACT)**

Participants will not be charged for any research related visits. All visits will be scheduled during standard post-transplant clinic visits. Twistle is a free service to participants.

23. Compensation

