We will compensate participants \$20.00 for each completed visit; three visits for participants randomized to usual care and thirteen visits for participants randomized to IMPACT intervention. IMPACT intervention participants will be given an additional \$20 for the in-depth interview at their last follow up visit. The payments will be issued at the completion of each visit in the form of a merchandise card.

24. Compensation for Research-Related Injury

If the subject becomes sick or injured as a direct result from the study, they may receive emergency treatment, however, there is no commitment by the UNM HSC to cover the costs related to research related injuries. The subject and/or their third party payer will be charged in the usual way.

25. Consent Process

We will obtain consent via a formal signed consent form. All potential participants will be given as much time as they need for consent review prior to signing the consent form and will be asked to verbalize the purpose of the study as a check for understanding. The consent form will then be signed and dated by the participant before initiation of any study activity.

Subjects not fluent in English

NA

Cognitively Impaired Adults/Adults Unable to Consent/Use of a Legally Authorized Representative

NA

Subjects who are not yet adults (infants, children, teenagers)

NA

Waiver or Alteration of Consent Process (consent will not be obtained, required element of consent will not be included, or one or more required elements of consent will be altered)

We are requesting a partial waiver of HIPAA Authorization for Screening/Recruitment. Pre-screening will include the following details:

- Received kidney transplant at the University of New Mexico
- Greater than 18 years of age
- Race/ethnicity details

PROTOCOL TITLE: **Improving Healthcare Outcomes in American Indian and Hispanic Transplant Recipients Using Culturally-Tailored Novel Technology (IMPACT)**

26. Documentation of Consent

A copy of the signed/dated ICF will be given to the subject. A copy of the signed/dated consent will be placed in the subject's research file that will be kept in a locked file cabinet. To document our consenting process we will be following the UNM HSC HRPO procedure titled, "SOP: Written Documentation of Consent (HRP-091)."

27. Study Test Results/Incidental Findings

NA

28. Sharing Study Progress or Results with Subjects

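### Every IMPACT participant is promised an in-depth interview, but it is tied to the last follow-up visit and nothing provides for those who leave before it

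*Combined protocol and SAP*

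**What the plan says.** **Who is interviewed.** Section 20 (Recruitment Methods): "All participants who are randomized to the IMPACT intervention will have in-depth interviews".

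**When.** The only timing is in Section 23 (Compensation), where IMPACT participants receive a further $20 "for the in-depth interview at their last follow up visit". The same section issues payments as each visit is completed, with thirteen visits in the IMPACT arm.

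**How.** Section 12 (Study Procedures) allows the interview to be held "either in-person, over the phone or via HIPAA compliant Zoom".

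**What it is for.** Section 12 directs it at the participant's experience and suggestions for improvement. Section 13 (Data Analysis) places it in the implementation evaluation, analysed by thematic coding, which is to inform the future large-scale project.

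**What acceptability is.** Section 1 (Aim 1a) and Section 7 (Study Endpoints) define it by patient ratings. In Section 7, "we will measure patients' satisfaction with the interventions with a revised version of the Client Satisfaction Questionnaire", "where higher satisfaction will indicate greater intervention acceptability", and the System Usability Scale is added, "where higher scores indicate ease of usability".

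**What happens to leavers.** Section 15 lets the investigator withdraw a subject for noncompliance, among other grounds. It lists three reasons for discontinuation (adverse event, noncompliance, protocol violation) and has all data destroyed for anyone who withdraws, whenever that happens. Section 13 says attrition and its reasons will be summarised when feasible.

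**The concern.** Section 20 sets the interview population as everyone randomised to IMPACT. Section 23 supplies an occasion that only those still attending at the end will reach. Nothing connects the two for a person who leaves at, say, month three: there is no trigger for an interview, no stated route for paying for one held outside a visit, and a rule that removes whatever that person has already given.

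In a pilot whose purpose is to decide whether and how to run a larger trial, the people who leave can say what drove them out. Section 15 has no category for leaving by choice or through dissatisfaction, so the coded reason for discontinuation would not capture this either. What is at stake is how representative the interview evidence is of those randomised, and whether the report shows how many were not heard.

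**Working it through.** **1. Which visit is the last one?** Section 12 gives weekly clinic visits in the first month (4), two-weekly visits for the next two months (4) and monthly visits in months 4-6 (3). Dietitian follow-up at 12 months adds one: 4 + 4 + 3 + 1 = 12. One early or in-hospital contact, which is an assumption, makes 13 and matches the thirteen visits in Section 23. Section 6 gives one year of participation. The last follow-up visit is therefore most naturally the 12-month visit, although Section 23 does not say so.

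**2. Who is reached, reading the sections together?**

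| Participant | Interview under the current text |
|---|---|
| Completes the programme and follow-up | Yes, at the last visit |
| Stops the diet and exercise programme but stays in follow-up | Yes, at the last visit |
| Leaves before the last visit | Promised by Section 20 and possible remotely under Section 12, but with no trigger, timing or payment route |
| Formally withdraws | As above, and Section 15 destroys what has been collected |

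The gap lies in the last two rows.

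**3. How much evidence is one person?** Inputs: 14-20 participants (Section 5) and nearly equal allocation (Section 3).

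- Arm size: 14/2 = 7 to 20/2 = 10.
- One person: 1/10 = 10% to 1/7 = 14%.
- Two people: 2/10 = 20% to 2/7 = 29%.

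This takes 14-20 as the number randomised. Section 5 also expects 33 × 0.80 = 26.4 consenters, printed as 26, which reproduces. If all 26 were randomised, the arm would be 13 and one person 1/13 = 7.7%. The 26 has no other bearing on this point.

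**4. Can an effect on a satisfaction figure be computed?** Not from the documents. The following is illustrative only. It applies to ratings, since the interviews produce themes and not a percentage. Let d be the share of the arm with no data, p_c the proportion satisfied among those who stay and p_s the proportion among those who leave.

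- All randomised: (1 − d) × p_c + d × p_s
- Error of the stayers-only figure: d × (p_c − p_s)

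With p_c = 0.90 (assumed), the error in percentage points is:

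| Arm | Missing | p_s = 0.90 | p_s = 0.60 | p_s = 0.30 |
|---|---|---|---|---|
| 7 | 1 | 0 | 4.3 | 8.6 |
| 7 | 2 | 0 | 8.6 | 17.1 |
| 7 | 3 | 0 | 12.9 | 25.7 |
| 10 | 1 | 0 | 3 | 6 |
| 10 | 2 | 0 | 6 | 12 |
| 10 | 3 | 0 | 9 | 18 |

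The range is 0 to about 26 points, and the sign reverses if p_s exceeds p_c. Direction and size come entirely from the assumed values.

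**The case against.** The strongest objection is that the endpoint is not touched. Acceptability is scored from the Client Satisfaction Questionnaire and the System Usability Scale, while the interviews feed a thematic evaluation. A reader might infer that, because interviews come last, acceptability is overstated, perhaps by 0.90 × 0.10 = 9 to 0.90 × 0.30 = 27 points if 10-30% leave and none of them is satisfied. The documents do not support that. Interview timing cannot move a questionnaire score, no dropout or satisfaction figure is given, and people may leave for reasons unrelated to liking the programme. This part of the objection stands in full.

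Second, Section 23 is a payment sentence and does not restrict who is interviewed. Section 20 covers everyone and Section 12 allows remote interviews, so it cannot be said that early stoppers are never interviewed. That also stands: someone who stops the intervention but remains in follow-up is covered. One might go further and read the phrase in Section 23 as each person's own last attended visit. That does not help, because for someone who drops out, that visit is known to be the last only afterwards.

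Third, other sources help: attrition reasons when feasible, a log of barriers, and periodic staff surveys. These partly cover the gap, but none is the leaver's own account.

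Fourth, questionnaire timing sits in a figure and an appendix not available here, so nothing can be said about whether ratings are collected before people leave. Section 15 would in any case destroy the ratings of those who withdraw. That is a problem with the destruction rule and not with interview timing.

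A reader might also want every interview moved to 6 months, because regular dietitian contact ends then. That shortens recall but loses months 6-12, including the 12-month dietitian follow-up. It is a trade-off and is not needed to close this gap.

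**Conclusion.** The point holds as a gap in provision. The plan promises an interview to all randomised to IMPACT, gives one occasion for it, and says nothing about those who leave before that occasion. The interview evidence would then come mainly from those who stay, with each missed participant worth 10-14% of it in an arm of 7-10. This rests on three readings: that the last follow-up visit is the 12-month visit, that 14-20 is the number randomised, and that the material not available here (the participant pathway figure and the appendices) contains no exit-interview procedure.

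No bias in the acceptability endpoint is shown, and none can be sized from the documents. The change is worth making because it is cheap and the arm is small.

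**What to change.** 1. **Sections 12, 20 and 23.** Keep the interview at the last follow-up visit for those who remain. Add that any IMPACT participant who stops the intervention or leaves early is offered the interview, and the satisfaction and usability questionnaires if not yet completed, by phone or Zoom shortly after stopping, with the same $20. State that this payment does not depend on a clinic visit.
2. **Section 15.** Separate stopping the intervention from withdrawing from the study. Amend the destruction rule so that exit data are kept with the participant's agreement. Without this change, an exit interview given on withdrawal would itself be destroyed. Align the consent text.
3. **Section 13.** Report how many of those randomised to IMPACT were not interviewed, and how many gave no ratings, beside the results.

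Cost: perhaps one to three additional phone interviews, or $20 to $60 in payments (1 × $20 to 3 × $20), plus the time to conduct and transcribe them, and a wording change to the withdrawal and consent text. Some who leave will decline, so the gap will narrow but may not close, which is why the count of those not reached should be reported.
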